3.0 SUMMARY

Protocol Number:	MPS-17IPVAW10
Protocol Title:	A Randomized, Single-Center, Blinded, Clinical Evaluation of the Antimicrobial Effectiveness of an Antimicrobial Cloth Compared to Vehicle and 0.9% Saline
Development Phase:	Phase 2
Product Intended Use:	Preoperative Skin Preparation
Planned Study Period:	May 2017 – July 24, 2017
Planned Sample Size:	24 evaluable treatments per each anatomical site per investigational product treatment arm
Objectives:	
Primary Objective : To compare the immediate antimicrobial activity of a thermally treated cloth impregnated with 0.4% w/v Octenidine Dihydrochloride in aqueous solution to thermally treated polyester cloths impregnated with vehicle formulation and polyester cloths containing 0.9% normal saline.
 
Secondary Objectives: To evaluate safety using skin irritation scores and the incidence of adverse events reported during the study.

Study Design:	This single site study is a randomized, blinded design employing a minimum of 36 healthy volunteers, where each subject receives two of the planned treatments on the abdomen and/or groin.
Study Population:	Healthy male and female volunteers, 18 years of age or older, with no dermatological conditions or known history of sensitivity to natural rubber latex, adhesive skin products (e.g., Band-Aids, medical tapes), polyester, octenidine dihydrochloride, or common personal care or beauty products will be enrolled into this study.
Study Product(s):	
Test Product: Thermally Treated Polyester Cloths Impregnated with 0.4% w/v Octenidine Dihydrochloride
 
Vehicle Control: Thermally Treated Polyester Cloths Impregnated with vehicle formulation.
 
Saline Control: 0.9% saline applied with Polyester cloths

Study Methodology:	ASTM Standard Test Method E1173-15, Evaluation of Preoperative, Precatheterization, or Preinjection Skin Preparations
Primary Study Endpoints and Acceptance Criteria:	For assessment of immediate activity at 10 min post application, a $> 1.2 \log_{10}$ superiority criterion is implemented for the mean treatment effect of the Investigational Product to the Vehicle Control and the Saline Control.
Secondary Study Endpoints and Acceptance Criteria:	Safety will be evaluated using skin irritation scores and the incidence of adverse events.

Protocol Number: MPS-17IPVAW10

Version: 1.0

Date: 05.25.17

Protocol Number:	MPS-17IPVAW10

4.0 LIST OF ABBREVIATIONS AND DEFINITION OF TERMS

AE	Adverse event
BD	Becton Dickinson and Company
cc	cubic centimeter
CFR	Code of Federal Regulations
CFU	Colony forming units
CI	Confidence Interval
CRF	Case Report/Record Form
CRO	Contract Research Organization
FDA	Food and Drug Administration
FDAAA	FDA Amendments Act of 2007
GCP	Good Clinical Practice
HIPAA	Health Insurance Portability and Accountability Act
ICH	International Conference on Harmonization
IRB/EC	Institutional or Independent Review Board/Ethics Committee
mL	Milliliter
mm	Millimeter
OCT	Octenidine Dihydrochloride
SAE	Serious Adverse Event
PHI	Personal Health Information
SD	Standard deviation
SOP	Standard Operating Procedure
TFM	Tentative Final Monograph
WHO	World Health Organization

5.0 INTRODUCTION

Prior to surgery or other invasive procedures, skin must be treated with a topical antimicrobial product to minimize the risk of nosocomial infection by reducing the number of microorganisms on the skin. The Food and Drug Administration (FDA) Tentative Final Monograph (TFM) for *Topical Antimicrobial Drug Products for Over-the-Counter Human Use; Tentative Final Monograph for Healthcare Antiseptic Drug Products* (Vol. 59, No. 116, June 17, 1994 pp 31448 to 31450) describes *in-vivo* procedures for evaluating this type of product. Consistent with the 1994 TFM and The 2015 FDA proposed changes to the TFM, 21 CFR Part 310, *Safety and Effectiveness of Health Care Antiseptics; Topical Antimicrobial Drug Products for Over-the-Counter Human Use; Proposed Amendment of the Tentative Final Monograph; Reopening of Administrative Record*; Proposed Rule (Vol. 80: No. 84, 1 May 2015. pp 25166 to 25205), recent letters published by the FDA on January 19, 2017 describe revised statistical analyses and expected performance criteria for antiseptic health care products tested in microbial log reduction studies.

Octenidine dihydrochloride (OCT) is an antiseptic agent that has a broad spectrum of activity against bacteria, yeast, and fungi. Its activity is persistent for hours to days after application, rendering it a suitable antimicrobial product to develop for use as a skin antiseptic.

The current study will evaluate the immediate antimicrobial efficacy of thermally treated polyester cloths impregnated with 0.4% w/v octenidine dihydrochloride in aqueous formulation to two negative controls, the thermally treated polyester cloth impregnated with vehicle formulation and a polyester cloth containing 0.9% normal saline, according to the revised statistical analyses and expected performance criteria published by the FDA on January 19, 2017.

6.0 OBJECTIVES

6.1 Primary Objectives

The primary objective of this study is to compare the immediate antimicrobial activities of a thermally treated polyester cloth impregnated with 0.4% w/v octenidine dihydrochloride in aqueous solution to thermally treated polyester cloths impregnated with vehicle formulation and a polyester cloth containing 0.9% saline. In agreement with the Food and Drug Administration Tentative Final Monograph (TFM) for *Effectiveness Testing of a Patient Preoperative Skin Preparation*, a log reduction study will be used to determine antimicrobial efficacy based on the statistical analyses outlined in published letters from the FDA on January 19, 2017. Testing will be performed according to the procedures outlined in the Food and Drug Administration Tentative Final Monograph (TFM) for *Effectiveness Testing of a Patient Preoperative Skin Preparation* (FR 59:116, 17 June 94, pp. 31450-31452). The test methods for this evaluation will be based on ASTM Standard Test Method E1173-15, *Evaluation of Preoperative, Precatheterization, or Preinjection Skin Preparations* and the test criteria from the deferral letters published by the FDA on January 19, 2017.

At 10 minutes post-prep, the test article should achieve a mean treatment effect $>1.2 \log_{10}$ greater than both negative controls on both the abdomen and the groin with 95% confidence. In this protocol two negative controls will be used, the Vehicle Control and the Saline Control.

6.2 Secondary Objectives

Safety will be evaluated using skin irritation scores and the incidence of adverse events.

7.0 STUDY DESIGN

7.1 Overall Study Design

This single site study is a randomized, blinded design employing a minimum of 36 healthy volunteers, where each subject receives two of the planned treatments on the abdomen and groin.

7.2 Specification of Study Endpoints

7.2.1 Primary Endpoints

The primary endpoints are the microbial counts for each product at the 10 minutes post-application time point for both the abdomen and groin.

7.2.2 Secondary Endpoints

The secondary endpoints are safety data including evaluations for skin reactions using the modified Berger Bowman irritation assessment scale and the incidence of adverse events reported during the study for all randomized subjects (the full Intent-to-Treat data set). Post treatment skin irritation scores of 3 on those scales are also considered adverse events.

7.3 Acceptance Criteria

The following table summarizes the minimum baseline criteria for each of the test sites and the expected minimum efficacy standards.

Table 3.3: Minimum Treatment Baseline and Expected Mean Log₁₀ Reduction per Anatomical Site

Anatomical Site	Treatment Day Baseline Criteria	Expected Efficacy Standards*
Abdomen	3.00 to 5.50 log ₁₀ /cm ²	At 10 minutes the mean treatment effect of the IP should be > 1.2 log ₁₀ the negative controls with 95% confidence
Groin	5.00 to 7.50 log ₁₀ /cm ²	At 10 minutes the mean treatment effect of the IP should be > 1.2 log ₁₀ the negative controls with 95% confidence

7.4 Treatment Allocation and Methods to Reduce Bias

7.4.1 Randomization

The randomization scheme for the study will be provided by the Study Sponsor. Subjects will be randomized to treatment using the following block design:

7.4.1.1 Treatment Balance

Each subject will receive two of the three possible treatments, one on the right side of the body and one on the left. A minimum of 36 evaluable subjects will be required to achieve a total of at least 24 test sites for groin and abdominal regions for each treatment.

The treatment assignments will be balanced such that the number of readings per anatomical site matches the calculated requirements.

7.4.1.2 Left/Right Balance

The application will be randomized so that each treatment is applied on an equal number of left and right sides of the body. Due to baseline requirements the final data set may be imbalanced with regard to right and left sides upon achieving the minimum number of qualifying body sites.

7.4.1.3 Site and Sample Time Balance

Each groin and abdomen sample site is divided into four areas and two of these areas are sampled once – one at baseline and one at 10 minutes ± 30 seconds, and two areas will not be used. Therefore, for any groin or abdomen site there are 24 possible sampling orders.

The number of subjects required for a completely balanced block design for all factors at once (study products, left/right, and sampling order) is a multiple of 144 (3*2*24). The exact subject numbers may make it infeasible to provide a completely balanced block design, so the following priority order will be used for design:

1. Treatment combinations will always be applied in balanced blocks, with the block size being sufficient to preserve the ratio of 1:1:1 for all three study products.
2. Left/right balance will be preserved – each treatment will be applied an equal number of times to each side of the body.
3. Sampling orders will be assigned in blocks of 24 as much as possible. If the final number of subjects is not a multiple of 24 the remaining subjects will be assigned random non-duplicative sample orders from the 24 possible sample orders.
4. The blocking will be adjusted based on the final subject numbers to be as balanced as possible with respect to all three factors above at once, with priority using the order listed above.

The Investigator is responsible for ensuring that the randomization is followed. A basic outline of a randomization schedule for the abdominal and groin sites is provided in Appendix 22.4. The final randomization schedule will be prepared by the study statistician before the initial treatment.

Subjects will be identified by their initials, and a subject number.

- Randomized subjects will be assigned numbers ranging from 001 to a three digit number equal to the total number of test subjects needed (36 for the estimated numbers).

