10.3.1 Preparation of Abdominal Test Area on Treatment Day

The test site within the abdominal region (abdominal test area) is defined as the area to the right and left sides of the abdomen, adjacent to the umbilicus that appear to be similar in condition and above the groin. Using a 5" x 5" sterile template, the corners of each abdominal test area will be marked directly on the skin using a non-toxic skin marker. Four sampling sites will be numbered within each abdominal test area, on each side of the abdominal region. The positioning and numbering of the abdominal sampling sites are standard for all subjects. Sampling sites on the contra-lateral side of the abdomen will be numbered in a mirror-image orientation. The four sampling sites within each abdominal test area represent one baseline (pre-prep) site, one post-prep sample sites (10-minutes) and two sites will be designated as not sampled.

Prior to performing the Treatment Day baseline sample collection, a skin irritation assessment will be performed by the Investigator or designee trained by the Investigator.

If an irritation score of 1 is assigned for any individual skin condition at the Treatment Day baseline, the subject will be excluded from the treatment phase of the study. After abdominal test areas are marked and sample sites numbered, baseline samples will be collected from the appropriate site per the randomization schedule in each test area using the Williamson-Kligman scrub cup technique.

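### Protocol 7.4.1.3 counts 24 sampling orders where its own layout allows only 12, so the 144 and the blocks of 24 built on that count need a minor correction

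*Protocol*

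**What the plan says.** Protocol 7.4.1.3 says that, of the four areas in each abdomen or groin test site, two are sampled once: "one at baseline and one at 10 minutes ± 30 seconds, and two areas will not be used". From this it infers: "Therefore, for any groin or abdomen site there are 24 possible sampling orders". It then gives the number of subjects needed to balance study products, left/right and sampling order completely, with the product in brackets: "is a multiple of 144 (3*2*24".

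Because that number may be infeasible, the section lists four rules in order of priority. Treatment balance comes first and left/right balance second. Rule 3 covers sampling order: "Sampling orders will be assigned in blocks of 24 as much as possible". When the total is not a multiple of 24, "the remaining subjects will be assigned random non-duplicative sample orders from the 24 possible sample orders". Rule 4 lets the blocking be adjusted to the final numbers "to be as balanced as possible with respect to all three factors above at once", keeping the same priorities. The planned number of subjects is given as "36 for the estimated numbers".

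Protocol 10.3.1 describes the abdominal area in the same way, with one baseline site and then "one post-prep sample sites (10-minutes) and two sites will be designated as not sampled". Protocol 10.3.2 repeats this for the groin. Appendix 22.4 gives an example schedule with four labels (baseline, 10 minutes, 30 seconds, 6 hours) and notes that the 30-second and 6-hour sites are not used in this study.

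**The concern.** The 24 does not follow from the description that precedes it. It would be right for four areas with four different roles, but here two areas share one role, that of not being sampled. Exchanging them changes nothing that is done to the subject and nothing that is measured.

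The count is used as well as stated. It fixes the multiple said to be needed for complete balance, and it sets the block size and remainder rule by which sampling positions are randomised. If a full set has 12 orders, the planned 36 subjects make up three full sets, and the protocol would be accepting a remainder that it does not need. What is at stake is how evenly the baseline and 10-minute samples are spread over the four positions.

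**Working it through.** **Inputs.** Four areas per test site, one baseline, one 10-minute and two unused (Protocol 7.4.1.3, 10.3.1, 10.3.2). Stated figures: 24 orders, 144 subjects, blocks of 24, 36 planned subjects (Protocol 7.4.1.3).

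**1. Reproducing the stated figures.** Four distinct labels on four areas give 4! = 24, and 3 × 2 × 24 = 144. Both are reproduced, but only if the two unused areas count as different.

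**2. Count under the plan's own layout.** There are four choices for the baseline area and three for the 10-minute area: 4 × 3 = 12, or 4!/2! = 12. Listing all 24 labelled arrangements and merging the two unused labels gives 12 placements, each occurring exactly twice.

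**3. Illustration from Appendix 22.4.** The 21 rows that can be read carry 21 different labelled orders but only 12 different (baseline, 10-minute) placements; nine occur twice and three once. R001 and R020, for example, both put baseline at Site 1 and 10 minutes at Site 2. The three labelled orders not among these rows would bring every placement to exactly two, so the split of nine and three shows only where the readable rows stop.

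**4. The product.** There are three treatment pairs (A with B, A with C, B with C) and two left/right arrangements of each, hence 3 × 2 = 6 ordered pairs. Fully crossing these with 12 orders takes 6 × 12 = 72 subjects. The stated 144 is sufficient but is twice that minimum.

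**5. What 36 subjects can do.** Protocol 7.4.1.3 names the factors as product, side and order. That gives 3 × 2 × 12 = 72 cells. Each subject receives two products, one per side, and so fills two cells if one order serves both sides, as in the rows of Appendix 22.4. The minimum is then 72/2 = 36 subjects. It can be attained: give six orders the left/right pairs A/B, B/C and C/A, and the other six B/A, C/B and A/C. Within each order every product appears once on the left and once on the right, so all 72 cells are filled once. Each ordered pair is used six times, so each unordered pair is used 6 + 6 = 12 times, as SAP 3.3 requires. This layout uses 36 of the 72 combinations of ordered pair and order, so it is balanced on the named factors but not fully crossed.

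**6. Rule 3 at 36 subjects.** With blocks of 24 there is one full block and a remainder of 36 − 24 = 12. With blocks of 12, 36 = 3 × 12 and there is no remainder. The 12 remaining subjects draw different labels from 24, but each real placement has two labels, so two different labels can be the same placement.

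**7. Full blocks of 24.** Each block uses every placement exactly twice. At totals that are multiples of 24, rule 3 is already balanced.

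**The case against.** The strongest reply is that the 24 is redundant rather than harmful. Full blocks of 24 are balanced, any multiple of 144 is balanced, and rule 4 tells the statistician to adjust the blocking for the best attainable balance. The final schedule is not in the documents, so nothing shows that an unbalanced one was produced. All of this stands, and it keeps the point minor. It does not make the stated count correct, and a statistician who relies on 24 would see a remainder at 36 where none need exist.

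Four stronger readings are tempting, and the documents do not support them:

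- A reader might infer that 72 is the only correct replacement for 144. It is the minimum only for full crossing of ordered pairs with orders. For product by side by order, 36 is enough.
- A reader might compute that, under rule 3 alone, the 12 remaining subjects cover all 12 placements with probability 2^12/C(24,12) = 4,096/2,704,156 = 0.15%, and conclude that the schedule is almost certainly unbalanced. That describes a procedure without rule 4, which the protocol does not use.
- A reader might treat the no-duplicates wording of rule 3 as a second failure. The rule asks for no repeats among the 24 listed orders, and a draw without replacement delivers that. The fault is the count.
- A reader might carry the correction over to the blocks of 24 subjects in Protocol 8.3. Those assign study products, and 24 = 4 × 6 is four full sets of the six ordered pairs. Nothing there depends on the number of sampling orders.

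It is also fair to say that no block size guarantees equal use of orders among evaluable sites. Subjects may enter for abdomen, groin or both (Protocol 8.0), and baseline plates are counted after product application, with replacements enrolled as needed (Appendix 22.2). The gain is in the randomised set.

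**Conclusion.** Protocol 7.4.1.3 is wrong as written, and the correction is minor. The layout allows 12 sampling orders against 24 stated. The protocol's own product becomes 72 against 144, on the reading that ordered treatment pairs are fully crossed with orders. The block rule leaves an avoidable remainder of 12 at 36 subjects, and drawing it from 24 labels can repeat a real placement unless this is put right under rule 4.

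This rests on one assumption, which Protocol 7.4.1.3, 10.3.1 and 10.3.2 support: the two unsampled areas have no separate role. That the 24 was carried over from a four-time-point template is plausible, since the example in Appendix 22.4 also shows a treatment code D that this three-arm study lacks, but it is an inference and the point does not need it.

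The consequence is confined to the balance of sampling position among randomised subjects, which the protocol ranks third. Sampling position is not a term in the primary model (Protocol 17.3.1, SAP 7.4.1). No effect on bias, treatment balance, left/right balance or the primary analysis is claimed.

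**What to change.** In Protocol 7.4.1.3:

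- State 12 sampling orders, and define an order as the pair (baseline position, 10-minute position).
- Replace 144 (3 × 2 × 24) with 72 (3 × 2 × 12), and say that this means full crossing of ordered left/right treatment pairs with orders.
- In rule 3, assign orders in blocks of 12 and draw any remainder without repeats from the 12. Use of the 12 orders then never differs by more than one among randomised subjects, and is equal at 36.

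The linked 36-subject layout shown above is an optional design choice and is not part of the correction. Protocol 8.3 needs no change on this account.

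The cost is a few words in one section and one block-size setting in the schedule, made before the first treatment. No extra subjects, procedures or analyses are needed.

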7.5 Masking/Blinding

Treatment materials for the following treatment groups will be blinded with treatment codes A or B:

- Thermally treated cloth impregnated with 0.4% w/v octenidine dihydrochloride aqueous solution (test article)
- Thermally treated cloth impregnated with vehicle formulation (Vehicle control)

The 0.9% Saline Control cannot be blinded due to product application requirements and will be assigned to treatment code C.

The staff member(s) performing product applications, sample collections, and irritation assessments will not be blinded from the identification of treatment assignments. Staff member(s) performing bacterial enumeration will be blinded from the identification of all treatment assignments. The study staff performing the bacterial enumeration will not be involved in the study material application, or the collection of samples or skin irritation assessments. The Raw Data Sheet sections of the case report

form will be maintained separately (from the pages within the case report form which include study treatment identifications) during the conduct phase of the study. The study staff performing the bacterial enumeration will record counts directly onto the Raw Data Sheet pages of the case report form without accessing the subject study documentation folder containing the other case report form pages. The Raw Data Sheets will be compiled with the entire case report form after all data recording has been completed.

7.5.1 Emergency Procedure for Unmasking

Response of medical personnel to an adverse event (AE) potentially associated with the test materials will not necessitate translation of the blinding code. The Sponsor Quality Assurance will provide the code translation to BSL Quality Assurance in the individual sealed envelopes (one for each blinded treatment code), which will be secured by BSL Quality Assurance and will remain unopened in the study file. If an emergency requires unblinding, the envelope corresponding to the treatment code (A-B) that is associated with the AE will be opened by the BSL Quality Assurance Manager to reveal the treatment identification for that single treatment. If possible, the Principal Investigator or designee will contact the Sponsor with notification of the intent to unblind the treatment codes prior to the actual unblinding. If it is not possible to notify the Sponsor prior to the unblinding, the Principal Investigator or designee will contact the Sponsor immediately following the unblinding procedure and follow with a written notification to document the exact manner in which the code was unblinded and the justification for the unblinding. The Principal Investigator or designee shall also provide written notification of the unblinding to the IRB. The BSL Quality Assurance Manager will communicate the treatment identification of the code associated with the AE to only the study personnel who require the information to manage the emergency.

